# 7.0 STATISTICAL CONSIDERATIONS

#### 7.1 Sample Size and Accrual

We will enroll 25 adult subjects with suspected with suspected kidney cancer and planned surgical nephrectomy. We have deep recruitment experience for kidney CEUS imaging. Approximately 150 nephrectomies for localized disease are performed at UNC yearly. Based on our previous recruitment rate of ~75% and a strong partnership with our urology colleagues, we anticipate no problems meeting our recruitment goal of 25 subjects.

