#### 7.1.1 Primary Objective

# 7.1.1.1 Predicting kidney mass diagnosis using 3D CEUS generated metrics.

The proposed sample of 25, assuming 60% clear cell legions, achieves 63.2% power to detect a difference of 0.1000 between a diagnostic test with an area under the ROC curve (AUC) of 0.8000 and another diagnostic test with an AUC of 0.9000 using a two-sided z-test at a significance level of 0.050. The correlation between the two diagnostic tests is assumed to be 0.9 for the positive group and 0.9 for the negative group.

The proposed sample of 25, assuming 60% clear cell legions, achieves 88.7% power to detect a difference of 0.1500 between a diagnostic test with an area under the ROC curve (AUC) of 0.8000 and another diagnostic test with an AUC of 0.9500 using a two-sided z-test at a significance level of 0.050. The correlation between the two diagnostic tests is assumed to be 0.9 for the positive group and 0.9 for the negative group.

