standard of histologic diagnosis to differentiate clear cell from non-clear cell tumors, we will use logistic regression to build predictive models based on multiple parameters from CEUS (WI, WO, MTT, TTP, PE and tumor volume), B-mode US images (length, echogenicity, shape), as well as patient factors (age, sex, race) (Table 1). We will assess the effects of individual parameters using hypothesis tests based on parameter estimates from the fitted logistic regression model. This approach facilitates assessment of the added value of the CEUS measurements over other patient factors. We will calculate nonparametric estimates and 95% confidence intervals for area under the curve (AUC) using the fitted logistic regression models, both with and without non-CEUS patient factors. We will use model selection procedures, including AUC, to identify a final model, with a one-sided test of AUC  $\leq .8$  vs AUC  $\geq .8$  at alpha=.05 for the final model. We will use model selection procedures based on optimizing AUC to identify a final model, with a one-sided test of AUC<=0.8 vs AUC>=.8 at alpha=.05 for the final model.

Gold Standard Comparator: Histologic diagnosis from pathologic tissue.

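### The one-sided test of AUC against 0.8 has no stated statistic or standard error; the usual default would run at about 12% type I error with 15 vs 10 patients, not 5%

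*Combined protocol and SAP*

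**What the plan says.** Section 7.2.1 builds logistic models for clear cell against non-clear cell histology, selects a final model by optimizing AUC, and ends the primary analysis "with a one-sided test of AUC<=0.8 vs AUC>=.8 at alpha=.05 for the final model". On estimation it says: "We will calculate nonparametric estimates and 95% confidence intervals for area under the curve (AUC) using the fitted logistic regression models". It does not give the test statistic, the variance formula, whether the standard error is taken at the estimate or at the null value, the scale, the interval method, or what happens if the observed AUC is 1.

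Section 7.1 fixes the size: "We will enroll 25 adult subjects". Section 7.1.1.1 assumes 60% clear cell, so 15 vs 10.

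Tests of AUC are described more fully in two other places, both for a different comparison. The power statement in 7.1.1.1 compares two correlated AUCs "using a two-sided z-test at a significance level of 0.050". Section 7.2.2 compares bolus with infusion by a Z-test with bootstrap standard errors.

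**The concern.** An AUC is bounded at 1, and its estimated standard error shrinks as the estimate approaches that bound. In a small sample, the datasets that overestimate the AUC therefore also have the smallest standard errors. A one-sided upper-tail test that divides by the estimated standard error is pushed towards rejection, and with 15 and 10 patients the push is large.

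The claim that the AUC exceeds 0.8 is the primary inferential claim of the study. If the statistic is left open, the analyst can choose it after seeing the data, and routine choices differ about threefold in their true error rate. The choice alone could decide the conclusion.

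**Working it through.** **Inputs.** Null AUC 0.8, one-sided, alpha 0.05 (7.2.1). n = 25 (7.1). 60% clear cell (7.1.1.1), so m = 0.60 × 25 = 15 and n = 10. Assumptions of this check: a fixed continuous marker with no fitting or selection, and equal-variance binormal scores unless stated otherwise.

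**The plan's own figures first.** Alpha 0.05 for the 0.8 test is a nominal level with no calculation behind it. The only computed figures are for the two-AUC comparison: "The proposed sample of 25, assuming 60% clear cell legions, achieves 63.2% power to detect a difference of 0.1000" and, for 0.80 vs 0.95, "achieves 88.7% power to detect a difference of 0.1500". The formula is

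power = Φ[(d − 1.96·SE0)/SE1], with SE0² = 2V(0.8)(1 − r) and SE1² = V1 + V2 − 2r√(V1·V2).

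- Hanley-McNeil variances with an AUC correlation r = 0.88 (a value chosen here): for d = 0.10, Φ[(0.10 − 1.96 × 0.0433)/0.0447] = 63.2%. For d = 0.15, Φ[(0.15 − 1.96 × 0.0433)/0.0541] = 88.6%.
- Obuchowski variances with the stated 0.9: 62.7% and 87.0%.
- Hanley-McNeil with 0.9 used directly as the AUC correlation: 70.3% and 91.6%.

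The stated figures are thus reproduced to within 2 points by a formula that takes the null variance at AUC 0.8.

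**Standard error at the null and at the estimate.** Hanley-McNeil: V(A) = [A(1 − A) + (m − 1)(Q1 − A²) + (n − 1)(Q2 − A²)]/(mn), with Q1 = A/(2 − A) and Q2 = 2A²/(1 + A).

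- At A = 0.8: Q1 = 0.6667 and Q2 = 0.7111. V = (0.160 + 14 × 0.0267 + 9 × 0.0711)/150 = 1.173/150 = 0.00782, so SE = 0.088.
- At A = 0.9: V = (0.090 + 14 × 0.0082 + 9 × 0.0426)/150 = 0.588/150 = 0.00392, so SE = 0.063.

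With the SE held at 0.088, rejection needs an AUC above 0.8 + 1.645 × 0.0884 = 0.946, that is 142 of the 150 patient pairs. With the SE taken at the estimate, 136 of 150 (AUC 0.907) is enough: (0.907 − 0.8)/0.0604 = 1.76. The same effect shows in simulation at true AUC 0.8: the mean DeLong SE falls from 0.115 in the lowest quarter of observed AUCs to 0.060 in the highest.

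**One-sided type I error at true AUC 0.8, nominal 5%, 15 vs 10 (simulation).**

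| Implementation | Rejection |
|---|---|
| Untransformed, DeLong SE | 12.0% |
| Untransformed, Hanley-McNeil SE at the estimate | 12.3% |
| Untransformed, bootstrap SE | 11.8% |
| DeLong SE, t(23) cut-off | 11.2% |
| Bootstrap 5% percentile bound | 9.0% |
| z-test, SE at AUC 0.8 | 3.9% |
| Logit scale, DeLong SE | 4.4-4.5% |

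**Sensitivity.** Over binormal scores with SD ratio 1, 1.5 or 0.67 and bi-exponential scores: DeLong 11.3-13.1%, Hanley-McNeil 11.5-14.1%, SE at the null 3.4-5.1%, logit 3.9-5.4%. Over case splits, DeLong gives 11.5% (13/12), 13.4% (17/8) and 12.7% (binomial split at 60%). The inflation is a small-sample effect: 8.1% at 60/40 and 6.6% at 150/100.

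**Interval.** An untransformed DeLong 95% interval runs above 1 in 42% of samples at true AUC 0.8 and in 84% at 0.9.

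**Power, 15 vs 10.**

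| True AUC | Untransformed DeLong (inflated level) | SE at 0.8 | Logit, AUC of 1 not counted | Logit, AUC of 1 counted |
|---|---|---|---|---|
| 0.90 | 52% | 28% | 27.5% | 27.5 + 2.5 = 30% |
| 0.95 | 85% | 63% | about 53-54% | about 54 + 11 = 65% |

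**What fitting adds (illustrative).** One marker with AUC 0.8, the rest noise, and the AUC taken in the fitting data:

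| Fitted predictors | Untransformed DeLong | Logit | SE at 0.8 |
|---|---|---|---|
| 3 | 22-23% | 10% | 9% |
| 6 | 45-48% | 25% | 23% |

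**The case against.** The strongest answer is that the 12% belongs to an implementation the plan never states. A reader might infer from the z-tests in 7.1.1.1 and 7.2.2 that the primary test is an untransformed z-test with an estimated standard error, and so that the plan's test has 12% error. The documents do not support that. Both sections concern the difference between two AUCs, and 7.2.2 specifies bootstrap standard errors only for the secondary comparison. A z-test with the standard error at 0.8 is also a z-test, and it holds its level. The plan's own power figures are reproduced by a formula with the null variance at 0.8. This objection stands in full against the stronger reading. It does not close the gap: that formula is for planning a different comparison and does not say how the 7.2.1 test will be done.

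A second objection is that a fixed marker is not this plan's test, which follows selection from 12 listed factors in the same 25 patients. That is also right. The 12% isolates one component and is not the plan's overall error rate.

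A third is that changing the standard error will not deliver 5% here. The fitted-model results above confirm this, so the change cannot be presented as a complete remedy.

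**Conclusion.** The point holds as one of under-specification with a measurable consequence. Section 7.2.1 sets a level of 5% but no test. The standard ways of supplying one have true levels from about 3.4% to 14% at 15 vs 10. The estimated-SE versions more than double the stated alpha (about 12%, range 11-14%), and the percentile bound nearly doubles it (about 9%). Two simple alternatives stay near 5%. These figures rest on the 60% clear cell planning assumption, on a fixed marker, and on the score distributions listed.

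Two stronger conclusions are not supported: that the plan prescribes a 12% test, and that choosing a better standard error would bring the primary test to 5%. Selecting and testing the final model in the same data is a separate and larger problem. The point is worth acting on because the correction is cheap and removes a choice that could otherwise be made after seeing the result.

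**What to change.** In 7.2.1, name the test of AUC against 0.8. Use either a z-test with the standard error evaluated at AUC = 0.8, or a test on the logit(AUC) scale. Give the 95% confidence interval on the logit scale. State the rule for an observed AUC of 1, where the logit is undefined, including whether it counts as rejection; at true AUC 0.95 about 11% of samples would meet it.

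The wording takes about a line and needs no extra patients or data. The cost is lower, honest power, as tabulated above: at 0.9, about 28-30% in place of an apparent 52%.

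Pair this with optimism correction or internal validation of the selected model. How the chosen test behaves on a corrected AUC is not shown here and should be checked by simulation before the analysis is fixed; that work is more than one line.

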# 7.2.2 Comparing diagnostic accuracy of F-R infusion imaging technique to low MI bolus imaging technique.

Image Analysis (Flash-Replenishment TIC analysis): For each 0.5-1 cm step, we will produce a TIC by delineating an ROI of the entire mass and measuring the mean contrast signal intensity over the time course of the F-R. We will model TIC using a mono-exponential equation, UI=A(1 -  $e^{-\beta t}$ ), where UI is ultrasound intensity and  $\beta$ , the slope of the tangent to the curve, represents the rate of perfusion. The height of the curve, A, represents the perfusion volume. To produce a single value for  $\beta$  for the entire tumor volume, we will calculate a weighted average based on the ROI area of the mass at each step. This value will serve as the WI rate.

Gold Standard Comparator: Histologic diagnosis from pathologic tissue.

*Statistical Analysis:* We will follow the model building and evaluation strategy used for the primary objective. This will be done separately for bolus and infusion imaging modalities, as well as combining the two multiparametric scores. We will compare AUCs from final logistic regression models obtained for bolus and infusion using a Z-test at alpha=0.05, with standard errors obtained by bootstrapping correctly adjusting for the fact that the two AUCs are calculated using the same data and hence correlated. We will conduct similar tests comparing the AUC based on the combined model to those based on bolus and infusion multiparametric scores separately. The proposed tests with sample size 25 have 80% power to detect a difference of .1 in the AUCs (0.8 vs 0.9) and 90% power to detect a difference of 0.15 (0.8 vs 0.95).

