#### 7.2 Data Analysis Plans

#### 7.2.1 Predicting kidney mass diagnosis using 3D CEUS generated metrics.

*Image Analysis (Low MI TIC analysis):* We will use Matlab (Mathworks, Natick, MA) for time intensity curve (TIC) analysis and 3D volume rendering. For each imaging plane, we will create a region of interest (ROI) by delineating the entire mass in the image slice. We will produce a TIC by taking the mean signal intensity in the ROI at each time point and calculate the metrics of wash-in rate (WI), wash-out rate (WO), mean transit time (MTT), time to peak (TTP) and peak enhancement relative to the surrounding parenchyma (PE) for each x-sweep position. A weighted average based on the ROI area at each position will be used to produce single values for the 3D volume for each TIC metric (WI, WO, MTT, TTP and PE). We will repeat this process for each plane of imaging.

3D volume rendering: We will also create 3D renderings of the tumor vasculature from the CEUS images. We will sort the image data collected over the 3-minute period after a bolus injection by the x- (or y-) sweep position, then by capture time in relation to the start of bolus injection through the wash-out period. We will produce a cumulative contrast image (CCI) at each position with the time-dependent image data by summing all time-dependent image data at each position. The images show where the microbubbles have travelled throughout the acquisition period, and since microbubbles are confined to the vascular spaces, the images provide excellent delineation of the vasculature. We will stack the CCIs together to create a 3D rendering.

Multiparametric score and statistical analysis: We will combine the

Table 1. Factors to be used in multiparametric score					
CEUS factors	B-mode factors	Patient factors			
WI, WO, MTT,	Length,	Age, sex, race			
TTP, PE, total	echogenicity,				
volume	shape				

quantitative data derived from CEUS image analyses into a single score. For the primary analysis using the gold

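### The bolus versus infusion comparison in 7.2.2 uses in-sample AUCs from models built on unequal numbers of metrics, so the estimated difference leans toward bolus

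*Combined protocol and SAP*

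**What the plan says.** Section 7.2.1 builds logistic models for clear cell versus non-clear cell histology and estimates the "area under the curve (AUC) using the fitted logistic regression models, both with and without non-CEUS patient factors". On selection it states: "We will use model selection procedures based on optimizing AUC to identify a final model".

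Section 7.2.2 carries this over to the comparison of techniques: "We will follow the model building and evaluation strategy used for the primary objective". The work is done separately for bolus and infusion and again for a combined score. The test is then set out: "We will compare AUCs from final logistic regression models obtained for bolus and infusion using a Z-test at alpha=0.05". A bootstrap enters at this point, described in these words: "with standard errors obtained by bootstrapping correctly adjusting for the fact that the two AUCs are calculated using the same data and hence correlated". That is the only use of resampling. Neither section describes a hold-out set, cross-validation, an optimism correction, penalisation or a limit on model size.

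The two techniques supply different numbers of inputs. Bolus yields "single values for the 3D volume for each TIC metric (WI, WO, MTT, TTP and PE" (7.2.1), and the process is repeated for each imaging plane. For infusion, the replenishment curve has two parameters. Beta is averaged to one tumour-level number: "This value will serve as the WI rate". Of the other, the plan says "The height of the curve, A, represents the perfusion volume". It does not say whether A is a candidate predictor or how the bolus planes are combined. Section 1.6 adds that infusion gives no wash-out rate.

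**The concern.** An AUC computed on the patients used to choose and fit the model is too high on average, and the excess grows with the number of candidate predictors. If both techniques offered the same number, the two excesses would largely cancel in the difference. With five metrics against one or two they do not, and bolus gains an advantage unrelated to its diagnostic value. A bootstrap used for the standard error describes the spread of this difference and does not remove the bias.

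The missing validation originates in 7.2.1. What is specific to 7.2.2 is the unequal counts. Objective 2.2.1 asks which technique is more accurate, and the answer would partly reflect how many metrics each one contributes. The combined-versus-single comparisons share the problem, because the combined model has the most candidates.

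**Working it through.** **1. The plan's power figure.** Inputs from 7.1.1.1: 25 patients, 60% clear cell (15 v 10), two-sided alpha 0.05, AUC 0.8 v 0.9 or 0.95, correlation 0.9 between tests. The Hanley-McNeil variance is

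V(A) = [A(1−A) + 14(A/(2−A) − A²) + 9(2A²/(1+A) − A²)] / 150.

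- V(0.8) = 0.00782, V(0.9) = 0.00392, V(0.95) = 0.00192.
- With an AUC correlation of 0.88 (back-solved; the plan does not state it), the null SD is √(2 × 0.00782 × 0.12) = 0.0433.
- The alternative SD is 0.0447 for 0.8 v 0.9 and 0.0541 for 0.8 v 0.95.
- Power = Φ((0.10 − 1.96 × 0.0433)/0.0447) = 63.2%, and Φ((0.15 − 1.96 × 0.0433)/0.0541) = 88.6%.

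The 63.2% and 88.7% of 7.1.2.1 therefore reproduce, but for two fixed scores. Nothing in the calculation allows for selecting and fitting models on the same 25 patients.

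**2. Size of the false lead.** Simulation with 15 v 10 patients. Bolus wash-in and infusion beta carry the same signal (within-class correlation 0.9), and every other metric is noise; this is our assumption. Tumour volume is in both models. 'Shared' adds the three B-mode and three patient factors to both. Entries are mean in-sample bolus minus infusion AUC.

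| True AUC | Model building | Predictors | 5 v 1 | 5 v 2 | 5 v 4 |
|---|---|---|---|---|---|
| 0.8 | all fitted | CEUS only | 0.074 | 0.054 | 0.017 |
| 0.8 | all fitted | shared | 0.054 | 0.036 | 0.008 |
| 0.8 | forward by AUC, no tight cap | CEUS only | 0.066 | 0.047 | 0.014 |
| 0.8 | forward by AUC, no tight cap | shared | 0.034 | 0.024 | 0.006 |
| 0.8 | forward, at most two predictors | CEUS only | 0.035 | 0.021 | 0.005 |
| 0.8 | forward, at most two predictors | shared | 0.014 | 0.011 | 0.004 |
| 0.9 | all fitted | CEUS only | 0.047 | 0.036 | 0.013 |
| 0.9 | all fitted | shared | 0.021 | 0.013 | 0.003 |

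Replicates: 2,000 (all fitted), 250 (forward, no tight cap), 500 (capped). Independent repeats agreed, with a highest value of 0.085 for 5 v 1 at AUC 0.8. With five metrics on each side the gap was −0.003 to +0.003, so the unequal count is the cause.

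**3. The same fitted models in new patients** (AUC 0.8, CEUS only, all fitted): −0.067 / −0.047 / −0.014. For 5 v 1 the in-sample comparison shows bolus ahead by 0.074 when its fitted model is behind by 0.067, a discrepancy of 0.141.

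**4. Planes entered separately** (AUC 0.8, CEUS only). Two planes give ten bolus metrics. Against beta and A the lead is about 0.10 to 0.12 with forward selection (60 replicates per setting) and about 0.136 with all fitted. Three planes, all fitted, reach 0.17 to 0.19.

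**5. Informative wash-out** (AUC 0.71 alone, so the best possible AUCs are 0.845 for bolus and 0.80 for infusion, a true gap of 0.045). The in-sample gaps are 0.104 / 0.085 / 0.048 for 5 v 1 / 5 v 2 / 5 v 4. The new-patient gaps are −0.017 / +0.001 / +0.036.

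**6. The Z-test with scores held fixed in the bootstrap** (5 v 1 or 5 v 2, all fitted; 1,500 replicates, 300 resamples). Bolus is wrongly favoured in 7–13% of trials at AUC 0.7, 3–6% at 0.8 and 0.5–2% at 0.9; infusion in 0.1% or less. A separate smaller run put 5 v 1, CEUS only, at 8.6% for AUC 0.8.

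**7. Combined model** at AUC 0.8: in-sample lead over infusion of 0.04 to 0.08 (5 v 1, 5 v 2), and over bolus of 0.001 to 0.014.

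**The case against.** **The size depends on assumptions.** This stands. The plan selects a final model, so the all-fitted rows are not exactly what it describes. Selection without a tight cap gives similar values with CEUS metrics only and smaller ones with shared factors. A two-predictor cap shrinks the lead further, and reading Section 1.6 as five versus four metrics leaves about 0.02 or less. However, 7.2.2 describes only beta and A, and the plan sets no cap.

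**The extra bolus metrics may be informative.** This also stands. Section 1.6 suggests that each bolus measurement may help predict subtype. In the informative five-versus-four case the in-sample gap (0.048) is close to the best possible gap (0.045). A reader might infer that any bolus lead would be spurious; the documents do not support that. The point is that an in-sample comparison cannot separate the real part from the artefact.

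**The test itself is not badly inflated.** A reader might infer a grossly inflated false-positive rate. With fixed scores, total error at AUC 0.8 is mostly near 5% and at 0.9 is below it. What is wrong is that almost all of it falls on the bolus side. Much higher rates arise if every resample refits the models and uses in-sample AUCs, but the plan does not say that it does.

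**It is a small study.** True, but the plan attaches a formal test and power figures to this comparison.

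**Conclusion.** The concern holds as a bias in the estimated difference. Followed as written, 7.2.2 compares in-sample AUCs after AUC-driven selection, and the result leans toward bolus whenever bolus brings more candidates. With equal true signal and noise elsewhere, the lean for five versus one or two metrics is roughly 0.02 to 0.09 at true AUC 0.8 and 0.01 to 0.05 at 0.9, under full fitting or selection without a tight cap. The planned difference is 0.10. No firm upper limit can be given, because the plan leaves the handling of planes open. The direction under this base case is secure; the size is not. It affects a secondary objective and can be corrected before analysis, so the plan should be changed, but the trial's design is not at fault.

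**What to change.** In 7.2.1 and 7.2.2:

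1. State the target as each technique's performance in new patients. Estimate AUCs and all AUC differences (bolus v infusion, combined v each) by repeated stratified cross-validation, with selection and fitting repeated in every training set and all models scored on the same held-out patients.
2. Prespecify a small or penalised candidate set per technique, including whether A is a candidate and how bolus planes are combined. Equal set sizes are an option, not a requirement: they remove the lean between equally informative techniques but may drop a useful metric.
3. Report the difference with its interval as the main result and treat the Z-test as descriptive. Name the resampling scheme for the interval in advance.
4. Label any in-sample AUC as such.

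**Cost.** SAP wording and computing; no new data.

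- AUCs will fall. At true AUC 0.8, bolus goes from 0.89 in-sample to 0.69 cross-validated with all CEUS metrics, or 0.77 with two.
- Cross-validation penalises a larger model fitted on 25 patients (about −0.07 for 5 v 1 at AUC 0.8), so step 1 without step 2 tilts the comparison the other way.
- Power is low. With two metrics each and held-out scores resampled, it is about 32% for 0.8 v 0.9, with total error of about 11% at AUC 0.7. With a standard error from repeating the whole procedure, it is about 2%, because that standard error is conservative (0.125 to 0.160 against an actual SD of 0.070 to 0.088).

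The power figures in 7.1.2.1 and 7.2.2 (which also disagree: 63.2% and 88.7% against 80% and 90%) should not be carried over to this analysis.

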#### 2.2 Secondary Objectives

- **2.2.1** To compare diagnostic accuracy of F-R infusion imaging technique to low MI bolus imaging technique.
- **2.2.2** To predict kidney mass stage using 3D CEUS-generated metrics

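### The bolus-versus-infusion AUC test does not hold non-technique terms equal in the two models, so a covariate kept in only one model can appear as a technique difference

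*Combined protocol and SAP*

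**What the plan says.** Section 2.2 sets the secondary objective: "To compare diagnostic accuracy of F-R infusion imaging technique to low MI bolus imaging technique".

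For this objective, the Statistical Analysis paragraph of Section 7.2.2 refers back to the primary analysis: "We will follow the model building and evaluation strategy used for the primary objective". It then adds: "This will be done separately for bolus and infusion imaging modalities, as well as combining the two multiparametric scores". The hypothesis test is attached to the end products: "We will compare AUCs from final logistic regression models obtained for bolus and infusion", by a Z-test at alpha 0.05 with bootstrap standard errors that allow for the correlation between the two AUCs.

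The strategy it refers to is in Section 7.2.1 and Table 1. The candidates are "multiple parameters from CEUS (WI, WO, MTT, TTP, PE and tumor volume"), together with "B-mode US images (length, echogenicity, shape), as well as patient factors (age, sex, race"). The selection rule is: "We will use model selection procedures based on optimizing AUC to identify a final model".

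Section 7.2.1 also provides AUC estimates and 95% confidence intervals with and without the non-CEUS patient factors. Neither section says which non-CEUS terms the bolus and infusion models must share.

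**The concern.** Age, sex, race and the B-mode findings do not depend on how the contrast was given. When selection runs separately for each technique with about 15 clear cell and 10 other tumours, the two final models can easily keep different subsets of these terms. The Z-test would then attribute to the technique a difference that partly belongs to, say, age or echogenicity. The bootstrap described handles the correlation between the two AUCs. It does not make the two models comparable in content.

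Section 1.6 says that the optimal approach is unknown, and this test is the study's direct evidence on that question. A difference that depends on which covariates happened to survive selection would be hard to interpret and could mislead the design of a later study.

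The plan also leaves open which contrast is being tested: the techniques by themselves, or what each adds to a common set of patient and B-mode information. The power statement is in terms of 0.80 against 0.90 or 0.95 and does not say which of these it means.

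**Working it through.** **Inputs.** From Sections 7.1.1.1 and 7.1.2.1: N = 25, 60% clear cell (15 and 10), two-sided alpha 0.05, correlation 0.9 in both groups, AUC 0.80 against 0.90 or 0.95, stated power 63.2% and 88.7%. *Assumption, not in the documents:* the AUC s of a covariate score that is independent of the technique score, shown over a range.

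**1. The plan's power figure.** Power = Φ((Δ − 1.96·SE₀)/SE₁), where SE₀² = 2V(0.80)(1 − r) and SE₁² = V₁ + V₂ − 2r√(V₁V₂), with the Obuchowski binormal variance. This gives V(0.80) = 0.00949, V(0.90) = 0.00528, V(0.95) = 0.00244 and SE₀ = 0.0436.
- Δ = 0.10: SE₁ = 0.0450, (0.10 − 0.0854)/0.0450 = 0.324, power 62.7%.
- Δ = 0.15: SE₁ = 0.0572, (0.15 − 0.0854)/0.0572 = 1.129, power 87.0%.

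Both are within two points of Section 7.1.2.1. Section 7.2.2 gives 80% and 90% for the same comparison. The two sections need reconciling, but nothing below depends on that.

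**2. Covariates kept in one model only, techniques equal at 0.80.** With equal-variance normal scores and independence, the best combination has AUC = Φ(√(z_t² + z_s²)), where z = Φ⁻¹(AUC) and z² = 0.7083 at 0.80.

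| s | z_s² | AUC with covariates | Gap from 0.80 |
|---|---|---|---|
| 0.60 | 0.0642 | 0.810 | 0.010 |
| 0.65 | 0.1485 | 0.823 | 0.023 |
| 0.70 | 0.2750 | 0.839 | 0.039 |
| 0.75 | 0.4549 | 0.860 | 0.060 |

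This is the extreme case: the whole score is in one model and absent from the other.

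**3. Can separate selection leave the models unequal?** In 600 simulated trials of 15 and 10, the techniques were equal (AUC 0.80, correlation 0.9). One shared term had AUC 0.65 and all other terms were noise. Selection was forward, by apparent AUC, using a least-squares score. Volume was treated as shared, and bolus had more technique metrics than infusion. The two models held different shared terms in 50% of trials (up to two terms) or 74% (up to three). The apparent AUC gap was at least 0.05 in 17% or 21%. These gaps mix unequal covariates, selection noise and the larger bolus metric set. They show that a gap can arise, not how much of it is due to covariates.

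**4. The same covariate score kept in both models.** The formula of step 2 is applied to both sides, with z² = 1.6424 at 0.90 and 2.7055 at 0.95. Power is from the formula of step 1, with r changed as the shared score implies (for example 0.907 at s = 0.70 for 0.80 against 0.90).

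| s | 0.80 vs 0.90 becomes | Power | 0.80 vs 0.95 becomes | Power |
|---|---|---|---|---|
| none | 0.100 | 62.7% | 0.150 | 87.0% |
| 0.60 | 0.094 | 59.6% | 0.142 | 83.8% |
| 0.70 | 0.078 | 51.6% | 0.119 | 74.1% |
| 0.75 | 0.067 | 46.8% | 0.103 | 67.3% |

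**The case against.** **The shared-terms case is not an error.** A reader might infer that common covariates bias the test toward no difference, or that the test fails to estimate what the objective asks. The documents do not support either reading. The objective speaks of diagnostic accuracy and Section 1.2 of predictive capabilities; neither restricts this to perfusion metrics in isolation. Comparing techniques on top of information that is routinely available is a legitimate question, and its smaller difference is the true incremental one. This objection stands. What remains is that the plan does not say which contrast is meant, and the power figures match the incremental one only if the 0.10 or 0.15 was defined that way.

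**The plan partly covers it.** Under Section 7.2.1, each technique's AUC would also be reported without age, sex and race. That is useful, but it does not mention B-mode terms and it carries no between-technique test. Section 7.2.1 also describes the score at one point as built from quantitative CEUS data, which could mean CEUS terms only; Table 1 and the model description point the other way. The wording is ambiguous rather than a settled choice.

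**Volume may be technique-specific.** Table 1 lists it under CEUS factors. Bolus imaging uses sweeps and infusion uses 0.5–1 cm steps, so each technique could measure its own. It should not be counted as common without a statement in the plan. Nor are all Table 1 metrics available to both techniques, because infusion gives no wash-out rate (Section 1.6).

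**The size rests on assumptions.** This stands. No covariate AUC is given, independence is assumed, and correlated terms could act differently. At covariate AUC 0.60 both effects are small. The level of power also depends on method: direct simulation of the paired test gave about 33–34% for 0.80 against 0.90, which has not been reconciled with the stated 63.2%. Only the direction of change should be taken from step 4.

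**Conclusion.** The concern holds in a limited form. Section 7.2.2 tests the AUCs of two separately selected models and does not require the same non-technique terms in both, so part of the tested difference can come from covariates. Under the illustrative assumptions (normal scores, independence, covariates wholly in one model, techniques equal at 0.80), that part is 0.01 to 0.06 for covariate AUC 0.60 to 0.75. For scale, the planned difference is 0.10 or 0.15. Partial overlap of covariates would be expected to give less.

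The shrinkage when both models share the same terms is a change of estimand to be stated, not a bias to be corrected. This is a secondary objective in a 25-subject study. The point is a worthwhile clarification at almost no cost and does not invalidate the analysis.

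**What to change.** In Section 7.2.2, state that the bolus-versus-infusion test uses two models with identical non-technique terms, in one of two ways:

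- **Technique-derived CEUS metrics only in both models.** This matches objective 2.2.1 and the powered contrast most directly.
- **One prespecified set of patient and B-mode terms forced into both models,** with selection limited to the technique metrics. This gives the incremental comparison.

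Name one as the main comparison and report the other as supportive. Say whether each technique measures its own tumour volume; if not, treat volume as a non-technique term. State which contrast the 0.10 and 0.15 differences refer to.

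The cost is SAP wording only, with no added subjects, imaging or data. The AUC reported for each technique may be somewhat lower than that of the freely selected models. The change does not remove the selection optimism that comes from bolus having more candidate metrics than infusion; that needs separate handling.
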